Iceland are eligible participants (n=661, m:f ratio=313:348). All children in public schools in the municipality are equipped with an iPad from 10 years of age. Exclusion criteria are diagnosis of severe disorder of intellectual development and/or physical-, developmental- and mental illness significantly restricting ability to use mobile apps. Research specifications and introduction to the application will be sent via email to parents and legal caretakers of all eligible participants through school officials along with confirmative survey link. If the link is answered, it yields confirmation for informed consent. Adolescents with informed consent from parents/legal caretakers will then invited to take part in the study through confirmative survey link. The study has been approved by the National Bioethics Committee (license number: VSNb2015060065/03-01).

Measurements

Original primary outcome measure will be app acceptability and functionality, measured with *Systematic Usability Scale* (SUS), a widely used and relatively well studied 10-item questionnaire on app usability where scores range from 0-100 and total score over 70 yielding satisfactory usability and user acceptance [40, 41]. Further primary measures were amount, frequency and time of daily physical activity measured through in-app activity, self-reported stress levels, quality of sleep and energy levels, measured through levels of the health app usage and completion of in-app health tasks.

Secondary outcome measures include standardized body mass index (*BMI-SDS*) based on BMI index reference values for Swedish children and adjusted for age and sex. Participants are weighed in kilograms in light clothing without shoes using a digital scale (Marel type C2; Marel, Reykjavik, Iceland). Height is measured in centimetres using a wall-mounted stadiometer (Seca stadiometer; Seca, Hamburg, Germany).

Anxiety and depressive symptoms will be assessed using the *Revised Children's Anxiety and Depression Scale* (RCADS), a self-report assessment tool for children and youth. The scale is a four point Likert scale, spans 47 questions and is divided into 6 subscales; separation anxiety symptoms, general anxiety symptoms, obsessive-compulsion symptoms, social anxiety symptoms, panic symptoms, depression symptoms. A *T*-score over 65 marks a clinical cut-off point. The inventory's psychometrics have been studied with acceptable findings in both US and Icelandic paediatric populations [42, 43].

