
Figure 1. Overview of app functions & categories

[figure not shown]

Procedure

The study is a randomized controlled study. Cluster randomization is used to distinguish three participating schools into control, treatment-as-usual (TAU) and intervention groups. Measures will be obtained at baseline and 42 days later. Participants in both the TAU group and the intervention group receive an approximately 10 minutes long introduction regarding the study specifications and the application. The control group receives no further contact, access to the application or information until study-end questionnaire measures. Participants in the intervention group are randomly assigned to teams consisting of 8 individuals that collectively and individually compete in point collection through completion of in-app health tasks. Participation in the TAU group and intervention group is defined as downloading the Sidekick app and completing at least 3 health exercises within it. Time of exercise is defined as the timestamp on completion of exercise within any of the three types of exercise categories (physical activity, nutrition and mental health) of the app. Exercise frequency refers to how often a given exercise was completed by a participant. Time of attrition was defined as the time stamp of last completing health exercise within the Sidekick throughout intervention period. The procedural difference between TAU group and intervention group evolves around motivational support. The intervention group receives weekly motivational support in form of individual and group feedback on usage, participation in friendly health task competitions and weekly altruistic rewards for usage. Participants in TAU group use the

application individually throughout trial period without any motivational support. A flow chart of participation is displayed in figure 2.

Figure 2. Participant flow chart

Statistical analysis

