Descriptive characteristics of participants along with attrition reason are reported. Pearson's correlation coefficient, independent samples *t*-tests, repeated measures ANOVAs with adjusted alpha levels, and χ^2 tests will be used to measure mean differences from baseline to trial's end within and between research groups on primary and secondary outcome measures. Kaplan-Meier survival analysis plots and logrank tests are deployed to assess time of attrition and possible significant differences between and within research groups [50, 51]. Trial beginning is defined as time of first in-app health exercise completion and the trial period was six weeks, or 42 days, from that moment. Attrition, or the event, is defined as the time of participants' last completed health exercise in SidekickHealth. Participants' cases will be evaluated as censored when the application was still being used 42 days after study start. Cox proportional hazard regression models with interacting covariables using research groups as clusters was used to examine attrition prediction based on usage of in-app health exercises between time, type and frequency of exercises as well as sociodemographic variables (age,

gender) [52]. Significance will be defined at $p < .05$. Data was analysed using IBM SPSS Statistics, Release Version 29 (SPSS, Inc., 2009, Chicago, IL, USA, <http://www.spss.com>).

References

1. Smith, A. (2015, April 1). *U.S. Smartphone Use in 2015*. Pew Research Center. <https://www.pewresearch.org/internet/2015/04/01/us-smartphone-use-in-2015/>
2. Silver, L. (2019, February 5). *Smartphone Ownership Is Growing Rapidly Around the World, but Not Always Equally*. Pew Research Center <https://www.pewresearch.org/global/2019/02/05/smartphone-ownership-is-growing-rapidly-around-the-world-but-not-always-equally/>
3. Anderson, M. & Jiang, J. (2018, May 31). *Teens, Social Media and Technology 2018*. Pew Research Center. <https://www.pewresearch.org/internet/2018/05/31/teens-social-media-technology-2018/>
4. Jones, E. A. K., Mitra, A. K. & Bhuiyan, A. R. (2021). Impact of COVID-19 on Mental Health in Adolescents: A Systematic Review. *The International Journal of Environmental Research and Public*, 18(5). <https://doi.org/10.3390/ijerph18052470>
5. Körmendi, A. (2016). Smartphone usage among adolescents. *Psychiatria Hungarica: A Magyar Pszichiátriai Társaság Tudományos Folyóirata*, 30(3), 297-302.

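### Seven unranked primary measures plus the attrition logrank are tested at p < .05, and the only alpha adjustment is unspecified and worded for the ANOVAs alone, so familywise error could reach about 30 to 34%

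*Combined protocol and SAP*

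**What the plan says.** The Measurements section opens with usability: "Original primary outcome measure will be app acceptability and functionality". It then widens the primary set: "Further primary measures were amount, frequency and time of daily physical activity measured through in-app activity", followed by "self-reported stress levels, quality of sleep and energy levels, measured through levels of the health app usage". That makes 1 + 3 + 3 = 7 primary measures. No order or hierarchy is given, and none is named as the one that decides the trial.

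The Statistical analysis section lists "Pearson's correlation coefficient, independent samples *t*-tests", then "repeated measures ANOVAs with adjusted alpha levels" and chi-square tests, to be applied "within and between research groups on primary and secondary outcome measures". Logrank tests on time of attrition and Cox models follow. The general rule is "Significance will be defined at $p < .05".

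Attrition is the first purpose stated at the end of the introduction, but it is not among the seven primary measures.

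On arms, the Procedure section says: "Cluster randomization is used to distinguish three participating schools into control, treatment-as-usual (TAU) and intervention groups". The same section gives the control group no access to the app.

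**The concern.** A trial with seven or eight candidate headline results, each judged at .05, has no fixed standard for success. Any nominally significant result could be presented as the primary finding, and a reader could not tell from the plan which test was meant to carry the conclusion.

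The adjustment phrase does not settle this, for two reasons. It is attached to one type of test, while several other types are applied to the same outcomes. And it cannot be carried out or checked, because it names no method, no set of tests and no resulting level. It may also miss most of the primary measures. The ANOVAs are listed for change from baseline to trial end, whereas usability and in-app activity have no value before the app is used. That last step is inference, but nothing in the wording excludes it.

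**Working it through.** **Inputs**

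- Per-test level 0.05 (Statistical analysis). Sidedness is not stated; two-sided is assumed.
- Seven primary measures (Measurements).
- One feasible contrast, TAU versus intervention, because control pupils have no app (Procedure).
- One further headline test, the between-arm logrank on attrition (Statistical analysis).
- Correlation between test statistics: not given. A common value from 0 to 0.9 is assumed.
- All null hypotheses true, and no adjustment applied to any of the tests counted.

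**Plan's own figure.** There is none to reproduce. The level is declared, and the plan gives no familywise error rate, power or sample-size calculation. The 661 is a count of eligible pupils.

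**Independent tests.** Familywise error = 1 − (1 − 0.05)^k.

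- k = 7: 1 − 0.95^7 = 0.302
- k = 8 (with logrank): 1 − 0.95^8 = 0.337

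**Correlated tests.** Simulation of k equicorrelated two-sided z-tests, 400,000 runs for each setting:

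| Assumed correlation | 7 tests | 8 tests |
|---|---|---|
| 0 | 30.2% | 33.7% |
| 0.3 | 27.1% | 30.0% |
| 0.5 | 22.9% | 25.0% |
| 0.7 | 17.8% | 19.2% |
| 0.9 | 11.4% | 11.9% |

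**Tests needed to pass 50%.** ln 0.5 / ln 0.95 = 13.5, so at least 14 independent tests.

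**After correction.** The equal-split threshold is .05/8 = .00625, and 1 − (1 − .00625)^8 = 4.9%. For seven tests it is .05/7 = .0071, again giving 4.9%. Holm starts from the same smallest threshold and keeps familywise error at or below 5% under any correlation.

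**Two separate allowances.** One test at .05 plus an independent family also controlled at .05 gives up to 1 − 0.95^2 = 9.75%. The two must therefore be joined.

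**The case against.** The best defence is that some adjustment is planned, and that 30% is a ceiling. Amount, frequency and time of activity come from the same in-app record, so the tests are probably correlated and the lower rows of the table are more realistic. Usability is described against a fixed benchmark of 70, so treating it as a between-arm test is a reading of the general wording; without it, six tests give 1 − 0.95^6 = 26.5%. Any primary measure analysed by an adjusted ANOVA would lower the figure further, by an amount that the plan does not allow anyone to compute. All of this stands. It reduces the size, but the error still exceeds twice nominal at correlation 0.9 for seven tests, and the rule remains unspecified.

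A reader might infer four stronger things that the documents do not support.

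- *A false-positive primary result is likely.* The range is 11 to 34%, below one half throughout.
- *Three arms multiply the primary and survival tests.* Seven measures over three pairwise contrasts would give about 60% for uncorrelated measures with the shared arms modelled. But the control school cannot supply app-based data. The third arm bears on the questionnaire scales, which are secondary.
- *The two alpha statements contradict each other.* An adjusted level is normally derived from a nominal .05. The text is incomplete, not contradictory.
- *About two false positives are expected among secondary scores.* Counting BMI-SDS, six RCADS subscales, GSE and five BEARS domains gives 13. Three contrasts make 39 tests, and 39 × 0.05 = 1.95. The plan does not say that each subscale or domain is tested separately, or that all three pairwise contrasts are run. The ANOVA adjustment would also most naturally apply to these scales.

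**Conclusion.** The concern holds in limited form. The plan has seven unranked primary measures and an eighth headline test on attrition. Its general level is .05, and its one adjustment is unspecified and worded only for the ANOVAs. On the TAU-versus-intervention contrast, the chance of at least one false-positive primary result is up to about 30% (34% with the logrank) if the tests are independent. For seven tests it is about 23% at correlation 0.5, 18% at 0.7 and 11% at 0.9. These figures assume two-sided, unadjusted tests and no true effects; the correlations are assumptions too. Within-group tests are not counted.

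The calculation also takes each single test to have a true 5% error. With one school per arm, that is doubtful for pupil-level tests. Assuming 661/3 ≈ 220 pupils per school (full uptake) and an intraclass correlation of 0.01 to 0.02, the design effect 1 + (220.3 − 1) × ICC is 3.19 to 5.39. A single between-arm test then has an error of about 27 to 40%. With 50 pupils per school it is about 11 to 16%. That is a separate problem, and multiplicity control does not cure it.

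**What to change.** Replace the general significance sentence with one familywise two-sided .05 covering the TAU-versus-intervention comparisons of the primary family, whichever test is used for each. Either of these would do:

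1. Holm across the seven listed primary measures plus the between-arm logrank, with smallest threshold .05/8 = .00625.
2. Time to attrition tested first at .05, as the first-stated aim. Go on to Holm across the seven (smallest threshold .0071) only if that test is significant.

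Do not spend a second, separate .05. Report secondary scales, within-group tests and Cox covariate tests as estimates with confidence intervals, labelled exploratory. State how the ANOVA adjustment fits this rule: its method, its family and its level.

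The cost is a stricter threshold, and so less power, for each primary measure. Both options also give attrition a confirmatory role that the Measurements section does not give it, so that section must change as well. Parts of the Statistical analysis section are in the past tense. If results have already been seen, moving attrition to the front would be a post hoc choice; option 1, which favours no single test, is then safer, and the timing should be disclosed.

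Because there is one school per arm, no between-arm test should be presented as having a true 5% error rate on the strength of this change alone.
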